5.2.5.2 Dermatological assessment

The entry criteria of the trial have been defined to exclude subjects with underlying dermatologic conditions that could impair the ability to detect a potential safety signal or might put the subject at increased risk.

Treatment continuation or discontinuation decisions will be made by the investigator considering the dermatologist's evaluation if applicable.

Forms to document skin assessments will be provided in the ISF, and data will be transferred into the eCRF.

5.2.6 Assessment of adverse events

Data and information necessary for the thorough assessment of AEs, SAEs, and AESIs will be reported to the sponsor via eCRF. This may include specific data and information not prospectively specified in this protocol.

5.2.6.1 Definitions of AEs

5.2.6.1.1 Adverse event

An AE is defined as any untoward medical occurrence in a trial participant or clinical investigation subject administered a medicinal product and which does not necessarily have to have a causal relationship with this treatment.

An AE can therefore be any unfavourable and unintended sign (including an abnormal laboratory finding), symptom, or disease temporally associated with the use of a medicinal product, whether considered related or not.

The following should also be recorded on the appropriate eCRF(s) if applicable:

- Worsening of the underlying disease or of other pre-existing conditions
- Changes in vital signs, ECG, physical examination and laboratory test results, if they are judged clinically relevant by the investigator

If such abnormalities already exist prior to trial inclusion, they will be considered as baseline conditions and should be collected in the eCRF only.

5.2.6.1.2 Serious adverse event

A serious adverse event (SAE) is defined as any AE, which fulfils at least one of the following criteria:

- Results in death
- Is life-threatening, which refers to an event in which the participant was at risk of death at the time of the event; it does not refer to an event that hypothetically might have caused death if more severe
- Requires inpatient hospitalisation or prolongation of existing hospitalisation
- Results in persistent or significant disability or incapacity
- Is a congenital anomaly/birth defect
- Is deemed serious for any other reason if it is an important medical event when based on appropriate medical judgement which may jeopardise the participant and may require medical or surgical intervention to prevent one of the other outcomes listed in

the above definitions. Examples of such events are intensive treatment in an emergency room or at home for allergic bronchospasm, blood dyscrasias or convulsions that do not result in hospitalisation or development of dependency or abuse

5.2.6.1.3 AEs considered “Always Serious”

In accordance with the European Medicines Agency initiative on Important Medical Events, Boehringer Ingelheim has set up a list of AEs, which by their nature, can always be considered to be “serious” even though they may not have met the criteria of an SAE as defined in Section [5.2.6.1.2](#). The latest list of “Always Serious AEs” can be found in the eDC system. A copy of the latest list of “Always Serious AEs” will be provided upon request. These events should always be reported as SAEs as described in Section [5.2.6.2](#).

Cancers of new histology and exacerbations of existing cancer must be classified as a serious event regardless of the time since discontinuation of the drug and must be reported as described in Section [5.2.6.2](#), subsections “**AE Collection**” and “**AE reporting to sponsor and timelines**”.

5.2.6.1.4 Adverse events of special interest

The term “adverse event of special interest” (AESI) relates to any specific AE that has been identified at the project level as being of particular concern for prospective safety monitoring and safety assessment within this trial, e.g. the potential for AEs based on knowledge from other compounds in the same class.

AESIs need to be reported to the sponsor’s Pharmacovigilance Department within the same timeframe that applies to SAEs; please see Section [5.2.6.2.2](#).

The following are considered as AESIs:

Potential Severe DILI

A potential severe Drug Induced Liver Injury (DILI) that requires follow-up is defined by any of the following alerts (alterations) of hepatic laboratory parameters:

For patients with normal transaminase levels (AST and ALT \leq 1 x ULN) at baseline:

- An elevation of AST (Aspartate Aminotransferase) and / or ALT (Alanine Aminotransferase) \geq 3-fold ULN combined with an elevation of total bilirubin \geq 2-fold ULN measured in the same blood sample, or in samples drawn within 30 days of each other, or
- ALT and / or AST elevations \geq 10-fold ULN.

For patients with abnormal aminotransaminase levels between > 1 and $< 3 \times \text{ULN}$ at baseline:

- An elevation of AST and / or ALT ≥ 3 -fold the baseline value combined with an elevation of bilirubin ≥ 2 -fold ULN or ≥ 2 -fold the baseline value (if bilirubin is elevated at baseline), measured in the same blood sample, or in samples drawn within 30 days of each other; or;
- Aminotransferase elevations ≥ 5 -fold the baseline value.

These lab findings constitute a hepatic injury alert and the patients showing these lab abnormalities need to be followed up according to the “DILI checklist” provided in the ISF. In case of clinical symptoms of hepatic injury (icterus, unexplained encephalopathy, unexplained coagulopathy, right upper quadrant abdominal pain, etc.) without lab results (ALT, AST, total bilirubin) available, the investigator should make sure these parameters are analysed, if necessary, in an unscheduled blood test. Should the results meet the criteria of hepatic injury alert, the procedures described in the DILI checklist should be followed.

Details on documentation and reporting are provided in the ISF.

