- 15 PK trough samples will be taken at all visits just before drug administration. Date and exact clock time of drug administration and blood sampling must be recorded in the eCRF. Further PK samples for PK profile will be taken at Baseline and at EOT according to PK sampling time schedule ([Appendix 10.2](#), PK time schedule). Patients will receive a PK-card at Visit 2 to support the recording of the exact clock time of medication intake for the previous two doses preceding PK sampling at subsequent visits.

16 [REDACTED]

17 [REDACTED]

- 18 Screening has to be registered in the Interactive Response Technology (IRT) system at time of informed consent to trigger initial medication supply to the site. The use of CFTR modulator therapy (CFTR-MT) has to be entered via the IRT module (CFTR-MT yes / no).
- 19 Randomisation V2: At randomisation the use of CFTR-MT has to be confirmed as stratification factor via the IRT module (CFTR-MT yes / no).
- 20 Patients should be instructed not to take their trial medication at home on scheduled visit days but bring it to the site and take it after respective pre-dose procedures have been performed.

TABLE OF CONTENTS

TITLE PAGE	1
CLINICAL TRIAL PROTOCOL SYNOPSIS	2
FLOW CHART	4
TABLE OF CONTENTS	7
ABBREVIATIONS AND DEFINITIONS.....	11
1. INTRODUCTION.....	15
1.1 MEDICAL BACKGROUND	15
1.2 DRUG PROFILE	17
1.3 RATIONALE FOR PERFORMING THE TRIAL	22
1.4 BENEFIT - RISK ASSESSMENT.....	23
1.4.1 Benefits	23
1.4.2 Risks	24
1.4.2.1 Risk related to the COVID-19 pandemic	27
1.4.3 Key safety data from clinical studies.....	28
1.4.4 Discussion.....	29
2. TRIAL OBJECTIVES AND ENDPOINTS.....	32
2.1 MAIN OBJECTIVES, PRIMARY AND SECONDARY ENDPOINTS.....	32
2.1.1 Main objectives.....	32
2.1.2 Primary endpoint	32
2.1.3 Secondary endpoint(s)	32
3. DESCRIPTION OF DESIGN AND TRIAL POPULATION	34
3.1 OVERALL TRIAL DESIGN	34
3.2 DISCUSSION OF TRIAL DESIGN, INCLUDING THE CHOICE OF CONTROL GROUP(S)	35
3.3 SELECTION OF TRIAL POPULATION	37
3.3.1 Main diagnosis for trial entry	38
3.3.2 Inclusion criteria	38
3.3.3 Exclusion criteria	39
3.3.4 Discontinuation of trial participants from treatment or assessments	41
3.3.4.1 Discontinuation of trial treatment	42
3.3.4.2 Withdrawal of consent to trial participation	43
3.3.4.3 Discontinuation of the trial by the sponsor	43
4. TREATMENTS.....	44
4.1 INVESTIGATIONAL TREATMENTS	44
4.1.1 Identity of the Investigational Medicinal Products.....	44
4.1.2 Selection of doses in the trial.....	44

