3.3.3 Exclusion criteria

Laboratory and medical examination:

1. Moderate or severe liver disease (defined by Child-Pugh score B or C hepatic impairment) or AST and/or ALT > 3.0x ULN at Visit 1
2. Estimated glomerular filtration rate (eGFR) according to CKD-EPI formula < 30 mL/min at Visit 1
3. Absolute blood neutrophil count < 1,000/mm³ (equivalent to < 1000 cells/µL or < 10⁹ cells/L) at Visit 1
4. Any findings in the medical examination (including BP, PR, or ECG) and/or laboratory value assessed at Visit 1 or during screening period that in the opinion of the investigator may put the patient at risk by participating in the trial
[Laboratory parameters from Visit 1 have to satisfy the laboratory threshold values as shown above. Visit 2 laboratory results will be available only after randomisation. In case at Visit 2 the results do no longer satisfy the entry criteria, the investigator has to decide whether it is justified that the patient remains in the trial. The justification for decision needs to be documented.]
5. Positive serological tests for hepatitis B, hepatitis C (also confirmed with HCV RNA), or human immunodeficiency virus (HIV) infection, or known infection status

Concomitant diagnosis and therapy:

6. A current diagnosis of:
 - a. Hypogammaglobulinemia
 - b. Common variable immunodeficiency
 - c. α1-antitrypsin deficiency being treated with augmentation therapy
 - d. Allergic bronchopulmonary aspergillosis being treated or requiring treatment
 - e. Tuberculosis or non-tuberculous mycobacterial infection being treated or requiring treatment according to local guidelines
[Laboratory tests (e.g. Quantiferon Gold test) may be performed at the discretion of the investigator]

Proprietary confidential information © 2023 Boehringer Ingelheim International GmbH or one or more of its affiliated companies

- f. Palmoplantar keratosis; or keratoderma climactericum
- g. Hypothyroidism, myxedema, chronic lymphedema with associated hyperkeratosis of the skin, acrocyanosis. If a subject has hypothyroidism but is treated and compensated, the subject is allowed into the trial
- h. Psoriasis affecting palms and soles; or body surface area for psoriasis $\geq 10\%$
- i. Reactive arthritis (Reiter's syndrome); keratoderma blennorrhagicum
- j. Pityriasis rubra pilaris
- k. Atopic dermatitis affecting palms and soles; or body surface area for atopic dermatitis $\geq 10\%$
- l. Active extensive verruca vulgaris, as per investigator's discretion

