- A CT must be available for confirmation of BE diagnosis at Visit 2. The scan may be historical (up to 5 years prior randomisation). If a new CT scan needs to be performed within the scope of the trial, this should happen (if a patient is otherwise eligible) during screening period before Visit 2. If applicable, accordance with local regulations regarding radiation exposure has to be ensured

The Screening Visit 1 can cover a period of up to 6 weeks, e.g., to wait for appointment at dentist, or if washout or stabilisation of certain medication is required (see [Section 4.2.2.1](#)). If the screening period of 6 weeks has to be exceeded for unforeseen reasons (e.g. scheduling dentist's appointment, infection) the sponsor has to be contacted immediately. In this case specific safety assessments have to be repeated prior V2 in an unscheduled visit (safety lab, physical examinations, vital signs, pregnancy testing, if applicable).

The Screening has to be registered in IRT to trigger the first medication shipment to the site.

In case eligibility of a patient is not confirmed, the patient will be registered as screen-failure. Re-screening would be allowed for screen-failed patients who are considered eligible at a later time point. Re-screening for a second time would be allowed if for independent reasons where one of these was an infection. These patients will receive a new patient number ([Section 3.3](#)).

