## **6.7 BASELINE, TIME WINDOWS AND CALCULATED VISITS**

For all parameters (except for biomarkers), baseline is defined as the last non-missing value prior to first administration of trial medication, or on the same date of first drug administration, if assessment times are not collected (e.g., vital signs, laboratory tests).

For specific assessments, multiple measurements are planned prior to first drug intake (e.g., at Visit 1 or 2). To derive the baseline, specific rules will apply as shown in [Table 6.7: 1](#).

According to CTP Section 5.4.1.3.2 Sputum sample collection at site, if sputum samples do not meet the sputum collection criteria as defined in the ISF/Lab Manual, it is generally possible that the patient returns the next day to provide the sputum sample. Baseline sputum measurement could be on or prior to the first drug administration + 1 day.

Table 6.7: 1 Derivation of baseline for assessments with multiple measurements prior to first drug administration

Parameter	Baseline value derivation
Biomarkers based on sputum	Mean of all available valid measurements collected up to date of first study drug administration + 1 day
Murray sputum colour chart	Last valid measurement collected up to date of first study drug administration + 1 day
NEATstik®	Mean of all available valid samples collected up to date of first study drug administration + 1 day

Measurements taken after first administration of trial treatment will be considered either on- or off-treatment values based on the definition in [Table 6.1.1: 1](#). Visit windowing will be performed as described in the tables below, in order to assign data to the relevant study visit based on the actual day of the assessment. Data will be analyzed using the re-calculated visits in the statistical tables. However, in the listings, all visits performed will be displayed (even if outside time-window), along with the re-calculated visit. The date of first treatment intake will be used as Study Day 1 for the time windowing. If more than one value is available within one time window the one which is closest to the planned time/day is used for analysis. In case two values are equidistant from the planned time/day, then the last one will be picked.

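### The alert for potential severe drug-induced liver injury has no numeric trigger for baseline AST or ALT at or above 3x ULN, although the protocol can admit and retain such patients

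*Protocol*

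**What the plan says.** Protocol Section 5.2.6.1.4 gives numeric alert criteria for two groups.

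- **Class 1**, AST and ALT at or below 1x ULN at baseline: alert at 3x ULN or more with bilirubin at 2x ULN or more, or at 10x ULN or more alone.
- **Class 2**, introduced as "For patients with abnormal aminotransaminase levels between > 1 and" and bounded above at less than 3x ULN: alert at 3 times the baseline value or more with raised bilirubin, or at 5 times the baseline value or more alone.

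Meeting the alert starts the DILI checklist and makes the event an AESI, reportable within 24 hours (Section 5.2.6.2.2). The section does not say which sample is baseline.

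Eligibility is set in Section 3.3.3. Exclusion criterion 1 removes "AST and/or ALT > 3.0x ULN at Visit 1". The bracketed text under criterion 4 says "Visit 2 laboratory results will be available only after randomisation". It continues: "In case at Visit 2 the results do no longer satisfy the entry criteria, the investigator has to decide whether it is justified" to keep such a patient, and "The justification for decision needs to be documented". No ceiling is given for a retained value.

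More than one pre-dose sample exists. The flow chart plans safety laboratory tests at Visits 1 and 2. If screening overruns 6 weeks, Section 6.2.1 adds another: "In this case specific safety assessments have to be repeated prior V2 in an unscheduled visit".

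For analysis, SAP Section 6.7 says "baseline is defined as the last non-missing value prior to first administration of trial medication" and names laboratory tests as an example. SAP Table 6.7: 2, which covers the safety laboratory, labels Visit 1 as Screening and Visit 2 as Baseline.

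**The concern.** The alert classes stop just short of where the entry rules stop. The exclusion uses a strict greater-than sign at 3.0x ULN and the alert uses a strict less-than sign at 3x ULN, so the boundary value passes the first and falls outside the second. The Visit 2 provision goes further, because it allows a patient above the limit to be dosed and followed.

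This matters because the risk table in Section 1.4.2 names Section 5.2.6.1.4 as the DILI mitigation, and Section 5.2.3 makes the additional hepatic measures depend on the criteria being met. For a patient in neither class, the start of the checklist and of AESI reporting rests on how the site reads the word baseline, on investigator judgement, or on instructions in the ISF.

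**Working it through.** The plan has no figure of its own to reproduce here. The check compares the baseline values the protocol permits with those the alert covers, then puts the triggers on the ULN scale.

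**1. Coverage.** Let x be baseline AST or ALT in multiples of ULN.

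- Covered by the alert: x ≤ 1 (class 1) and 1 < x < 3 (class 2).
- If baseline is Visit 1, eligible values are x ≤ 3.0. Uncovered: x = 3.0 only. With an assumed ULN of 40 U/L this is 3 × 40 = 120 U/L.
- If baseline is the last pre-dose value, Visit 2 is limited only by the investigator's documented decision. Uncovered: every retained x ≥ 3.0, with no upper limit.

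A patient entered in error with a Visit 1 value above 3.0x ULN may also be kept after a benefit-risk assessment (Section 3.3), and would be uncovered under either reading if the value is still that high at Visit 2.

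**2. Which sample is baseline.** SAP Section 6.7 and Table 6.7: 2 point to the last pre-dose value, normally Visit 2. Flow chart footnote 15 also uses the term for Visit 2, but only for PK: "Further PK samples for PK profile will be taken at Baseline and at EOT". The alert text refers to none of these.

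**3. Class 2 triggers on the ULN scale.** With raised bilirubin the trigger is 3 × x; alone it is 5 × x.

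| Baseline (x ULN) | With raised bilirubin | Alone | Status in current text |
|---|---|---|---|
| 2.0 | 6.0 | 10.0 | covered |
| 2.8 | 8.4 | 14.0 | covered |
| 3.0 | 9.0 | 15.0 | no class |
| 3.4 | 10.2 | 17.0 | no class |
| 4.0 | 12.0 | 20.0 | no class |

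The last three rows show what class 2 would give if its upper bound were deleted. Coverage then becomes x ≤ 1 and x > 1, with nothing left out. For a given baseline value this only adds triggers; no existing one moves. The added triggers are high. A cap at the values for x = 3.0, that is 3 × 3.0 = 9x ULN with raised bilirubin or 5 × 3.0 = 15x ULN alone, would join class 2 without a jump.

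**4. Effect of naming the baseline sample.** These are illustrative patients.

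| Visit 1 → Visit 2 (x ULN) | Trigger, Visit 1 baseline | Trigger, last pre-dose baseline |
|---|---|---|
| 1.0 → 2.5 | 3 / 10 (class 1) | 3 × 2.5 = 7.5 / 5 × 2.5 = 12.5 |
| 2.8 → 0.9 | 8.4 / 14 | 3 / 10 (class 1) |
| 2.8 → 3.4 | 8.4 / 14 | none now; 10.2 / 17 with the bound deleted; 9 / 15 with the cap |

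Each pair is the trigger with raised bilirubin, then alone. A last pre-dose baseline raises the trigger for patients whose values rise between visits and lowers it for those whose values fall. The first two rows need no value at or above 3x ULN, so this effect reaches beyond the gap itself.

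**The case against.** The strongest reply is that very little turns on this. On a Visit 1 reading the gap is one boundary value. A Visit 2 value above the limit has already prompted a documented decision. Liver tests are repeated at Weeks 1, 4, 8 and 12. Clinically relevant laboratory findings are AEs (Section 5.2.3), and important medical events and events on the sponsor's always-serious list are SAEs with 24-hour reporting, though that list was not available. Treatment stops for serious or severe DILI attributable to the drug (Section 3.3.4.1), the DMC reviews safety data, and the Hy's Law listing in SAP Section 7.8.2 does not use baseline. The ISF holds the DILI checklist and reporting details and may already cover these patients.

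That stands as to size. It does not close the gap in the protocol text. The Hy's Law listing is a reporting output and gives sites no instruction. The DILI item among the stopping rules refers back to Section 5.2.6.1.4, and the symptom route within that section ends by asking whether the same numeric criteria are met.

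Two further objections also stand. Laboratory baseline is defined for the analysis, so what is unclear is confined to the alert. And naming the last pre-dose value as baseline has a real cost for patients whose values rise before dosing.

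A reader might infer that liver injuries in these patients would go unreported. The documents do not support that: what is absent is a numeric trigger, and the other routes remain open.

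**Conclusion.** The gap is real and calls for a minor safety-rule correction. The alert in Section 5.2.6.1.4 has no numeric trigger for baseline AST or ALT at or above 3x ULN, while Section 3.3.3 admits exactly 3.0x ULN at Visit 1 and allows higher Visit 2 values to be retained.

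Few or no patients among 24 are likely to be affected. The documents give neither the rate of retained values at or above 3x ULN nor the rate of later rises, so no probability of a missed alert can be stated. The protocol does not expect BI 1291583 to add to the liver risk of modulator therapies (Section 1.4.4). The sample size and the planned primary and secondary analyses are unaffected.

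The conclusion rests on the visible protocol text; the ISF could narrow the practical consequence. A reader might also infer that exclusion criterion 1 must change to match the alert. It need not: once class 2 has no upper bound, the value 3.0x ULN is covered.

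**What to change.** 1. In Section 5.2.6.1.4, delete the upper bound of the second class so that it applies to any baseline above 1x ULN. Every dosed patient then has a trigger.
2. Check that the DILI checklist in the ISF matches. If it already covers these patients, align the protocol text with it.
3. Optionally, cap the trigger for baselines at or above 3x ULN at 9x ULN with raised bilirubin or 15x ULN alone. The sponsor should judge this clinically.
4. Preferably, state in the same section which sample is baseline. The last value before the first dose would agree with the SAP laboratory rule. The sponsor should accept the trade-off knowingly: against a Visit 1 baseline, a patient going from 1.0x to 2.5x ULN moves from 3x/10x to 7.5x/12.5x ULN, while a patient whose values fall is alerted earlier.

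Leave exclusion criterion 1 as it is. The cost is one or two short wording changes and a document check, with no new test or visit. As a protocol change it needs ethics committee and competent authority approval (Section 8.1), so it fits best in the next amendment.

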5.2.6.1.5 Intensity (severity) of AEs

The intensity (severity) of the AE should be judged based on the following:

Mild:	Awareness of sign(s) or symptom(s) that is/are easily tolerated
Moderate:	Sufficient discomfort to cause interference with usual activity
Severe:	Incapacitating or causing inability to work or to perform usual activities

5.2.6.1.6 Causal relationship of AEs

Medical judgement should be used to determine the relationship between the adverse event and the BI investigational compound, considering all relevant factors, including pattern of reaction, temporal relationship, de-challenge or re-challenge, confounding factors such as concomitant medication, concomitant diseases and relevant history.

Arguments that may suggest that there is a reasonable possibility of a causal relationship could be:

- The event is consistent with the known pharmacology of the trial drug
- The event is known to be caused by or attributed to the drug class
- A plausible time to onset of the event relative to the time of drug exposure
- Evidence that the event is reproducible when the drug is re-introduced
- No medically sound alternative aetiologies that could explain the event (e.g. pre-existing or concomitant diseases, or co-medications)
- The event is typically drug-related and infrequent in the general population not exposed to drugs (e.g. Stevens-Johnson syndrome)

- An indication of dose-response (i.e. greater effect size if the dose is increased, smaller effect size if dose is reduced)

Arguments that may suggest that there is no reasonable possibility of a causal relationship could be:

- No plausible time to onset of the event relative to the time of drug exposure is evident (e.g. pre-treatment cases, diagnosis of cancer or chronic disease within days/weeks of drug administration; an allergic reaction weeks after discontinuation of the trial drug concerned)
- Continuation of the event despite the withdrawal of the medication, considering the pharmacological properties of the compound (e.g. after 5 half-lives)
Of note, this criterion may not be applicable to events whose time course is prolonged despite removing the original trigger
- There is an alternative explanation, e.g. situations where other drugs or underlying diseases appear to provide a more likely explanation for the observed event than the drug concerned
- Disappearance of the event even though the trial drug treatment continues or remains unchanged

